## Clinical Investigation Plan

### 6.2.2 Assessments

The following will be collected during the Infirmity Programming visit:

- Infirmity programming data, programming parameters, duration of programming and program impedance.
- Programmer satisfaction survey
- Programmer Experience

### 6.3 Follow-up Assessments

#### 6.3.1 Follow-up for All Subjects (Site Visit)

Follow-up visits are scheduled at 3 and 6 months after the Infirmity Programming visit. If Infirmity Programming is performed over back-to-back days, then follow-up visit timing is based on the date of the second day of programming.

At each visit, the following procedures and assessments must be completed:

- Quality of life assessment
- Motor symptom evaluation (stimulation ON/medication ON) performed by a blinded assessor
- Medication (only PD or ET medications)- indicate the drug category the subject is currently taking on a long-term basis, i.e. no short-term medication
- Interrogation of programmed settings and program impedance.

The quality of life assessment must be performed prior to the motor symptom evaluation. Motor symptom evaluation will be performed by a blinded assessor, who will not be aware of the subject's programming.

If in the Investigator's opinion, the selected DBS electrode contact configuration does not provide adequate therapy for the subject at a follow-up visit, the subject's DBS system parameters can be adjusted. by re-programming with the Infirmity tool. This re-programming should be performed using the same procedure detailed in Section 6.2.1, and by the same programmer who programmed the patient during the Infirmity Programming visit. If re-programming is performed, motor symptom evaluation must be performed before and after re-programming at the follow-up visit.

An unscheduled visit is defined as any visit that occurs outside of a specified study visit related to an adverse event or withdrawal of the patient from the study. Any routine programming that occurs outside of a study visit will be captured at the subsequent study visit. Any unscheduled visit needs to be documented by completing the Unscheduled Visit form and other appropriate forms if applicable (Adverse Event, Withdrawal, Programming, and Medication).

#### 6.3.2 Patient Reported Outcome (PRO) Measures

The coordinator or designee will administer patient-reported outcome questionnaires. It is important the subject understands the meaning of all words and instructions in the questionnaires. The subject should be instructed to ask any questions about the questionnaires if further explanation is needed. Once the questionnaires are completed, the Coordinator or designee will review for completeness to verify that all questions have been answered according to the directions provided.

The following PRO measures will be collected according to the CIP requirements (Sections 6.1.1 and 6.3.1):

- Parkinson's Disease Questionnaire (PDQ-39)

*This confidential document is the property of Abbott and shall not be reproduced, distributed, disclosed or used without the express written consent of Abbott*

## Clinical Investigation Plan

- Quality of Life in Essential Tremor Questionnaire (QUEST)

The Parkinson's Disease Questionnaire (PDQ-39) is a widely used validated questionnaire used to measure PD specific health status [18]. The self-administered questionnaire consists of 39 questions and takes approximately 10-20 minutes to complete with paper & pencil. The subject is instructed to answer one of five response categories depending on how often (from never to always) they have experienced the problem addressed by each item during the past month due to PD. There is a total of 8 dimensions that represent mobility, activities of daily living, emotional well-being, social support, cognition, communication and bodily discomfort. For each question, a 5-point ordinal scoring system is assigned (0 to 4), and the results are summed across all questions and scaled to a 100-point system. Lower scores reflect a better quality of life.

The Quality of Life in Essential Tremor Questionnaire (QUEST) is a disease-specific assessment used to measure the quality of life of ET patients [19]. The self-administered questionnaire consists of 30 questions and is completed with paper & pencil. The subject is instructed to answer one of five response categories depending on the frequency (from never to always) with which tremor was found to impact functional activity or was associated with specific feelings. For each question, a 5-point ordinal scoring system is assigned (0 to 4). The 30 items are divided into five sub-scales (physical/ADL, psychosocial, communication, hobbies/leisure, and work/finances), and the score for each sub-scale is expressed as a percentage of the total score possible for that sub-scale. Lower scores reflect less dissatisfaction or disability due to essential tremor.

### 6.3.3 Schedule of Events

CIP Activity	Enrollment	Baseline	Informity Programming (21±7 days since Baseline)	3 Months (±30 days) since Informity Programming	6 Months (±30 days) since Informity Programming
Informed Consent Signed	X				
Inclusion/Exclusion Criteria Check	X				
Subject Demographics		X			
Disease History		X			
Baseline Programming		X			
Programmer Experience			X		
Medication		X		X	X
Motor Symptom Evaluation		X		X	X
Quality of Life Evaluation		X		X	X
Implant Information		X			
Images Collected		X			
Informity Programming			X		
Satisfaction			X		
Device interrogation and impedance measurement				X	X
Adverse Event	If applicable				
Deviation					

*This confidential document is the property of Abbott and shall not be reproduced, distributed, disclosed or used without the express written consent of Abbott*

## Clinical Investigation Plan

Withdrawal	
Product Out of Service	

### 7.0 **ADVERSE EVENTS**

To comply with worldwide standards and guidelines on clinical study adverse event reporting, the Sponsor has adopted uniform and worldwide applicable standard definitions and reporting timelines to be used and adhered to by the investigators.

#### 7.1 **Definition**

##### 7.1.1 **Adverse Event**

An adverse event (AE) is any untoward medical occurrence, unintended disease or injury, or untoward clinical signs (including abnormal laboratory findings) in subjects, users or other persons, whether or not related to the medical device under investigation.

**Note 1:** This definition includes events related to the medical device under investigation.

**Note 2:** This definition includes events related to the procedures involved.

**Note 3:** For users or other persons, this definition is restricted to events related to medical devices under investigation.

##### 7.1.2 **Serious Adverse Event**

If the AE meets any of the criteria below, it is regarded as a serious adverse event (SAE).

- a) Led to a death,
- b) Led to a serious deterioration in health of the subject, that either resulted in
  1. a life-threatening illness or injury, or
  2. a permanent impairment of a body structure or a body function, or
  3. in-patient hospitalization or prolongation of existing hospitalization, or
  4. medical or surgical intervention to prevent life threatening illness or injury or permanent impairment to a body structure or a body function, or
  5. chronic disease
- c) Led to fetal distress, fetal death or a congenital abnormality or birth defect.

**Note:** A planned hospitalization for pre-existing condition, or a procedure required by the CIP, without a serious deterioration in health, is not considered to be an SAE.

#### 7.2 **Device Relationship**

Determination of whether there is a reasonable possibility that an investigational product or device under investigation caused or contributed to an AE is to be **determined by the investigator** and recorded on the appropriate CRF form. Determination should be based on assessment of temporal relationships,

## Clinical Investigation Plan

evidence of alternative etiology, medical/biologic plausibility, and patient condition (pre-existing condition).

### 7.3 Adverse Event

#### 7.3.1 Adverse Event Reporting

Safety surveillance and reporting starts as soon as the patient is enrolled in the clinical study. Safety surveillance and reporting will continue until the last follow-up visit has been performed, the subject is deceased, the subject concludes participation in the clinical study or the subject withdraws from the clinical study. All applicable adverse event data will be collected throughout the time period defined above and will be reported to the Sponsor on a CRF. Additional information with regard to an adverse event should be updated within the appropriate CRF.

Unchanged, chronic, non-worsening or pre-existing conditions are not AEs and should not be reported.

All reportable adverse events will be collected on each subject through the 6-month follow-up visit, when each subject's participation in the study ends.

Clinical Site	Reporting timelines
All Sites	Serious adverse events must be reported to the Sponsor no later than 3 calendar days from the day the site personnel became aware of the event or as per the investigative site's local requirements, if the requirement is more stringent than those outlined.

The date the site staff became aware the event met the criteria of an SAE per protocol must be recorded in the source document. The Investigator will further report the SAE to the local IRB according to the institution's IRB reporting requirements.

Records related to the subject's subsequent medical course must be maintained and submitted (as applicable) to the Sponsor until the event has subsided or, in case of permanent impairment, until the event stabilizes and the overall clinical outcome has been ascertained. Adverse events will be monitored until they are adequately resolved. The status of the subject's condition should be documented at each visit.

Reportable events to sponsor are considered:

- All adverse events related to the device, stimulation, and/or procedure regardless if serious or non-serious
- All death events

For unexpected failure modes or unexpected AEs, the site should follow their standard reporting practices for medical device reporting (MDR). As defined in 21 CFR 803, a MDR reportable event (or reportable event) is an event that device user facilities become aware of that reasonably suggests that a device has or may have caused or contributed to a death or serious injury. A device user facility must report deaths and serious injuries that a device has or may have caused or contributed to; establish and maintain AE files, and submit summary annual reports to FDA.

## Clinical Investigation Plan

**Complaints reporting:** A complaint is defined as a deficiency related to its identity, quality, durability, reliability, safety, effectiveness or performance of a device after it is released for distribution. All device complaints/malfunctions should be reported to the Sponsor's Customer Service Department.

If the complaint does not involve an AE, the investigator must notify the Abbott Post Market Surveillance Department by submitting the complaint information via email to [contact] or by [contact] as soon as possible after becoming aware of the complaint.

### 7.3.2 Procedure for Recording and Reporting Subject Death

Should death occur, the investigator is requested to record death information in the hospital records and document the information on the Adverse Event CRF and submit to Sponsor per the serious adverse events reporting requirements stated in the 'Adverse Event Reporting Requirements' section (7.3.1).

- All efforts to obtain the details about the circumstances surrounding the patient death should be made by the Investigator.

The subject's death is an early conclusion of the subject's participation in the clinical investigation. Therefore, the Investigator is required to complete the Withdrawal CRF.

## 8.0 STATISTICAL CONSIDERATIONS

The following section describes the statistical methods for the clinical study. Additional details on statistical analyses, including justification of clinical study design, sensitivity analyses, poolability analyses, subgroup analyses and analysis of descriptive endpoints, may be maintained in a separate Statistical Analysis Plan (SAP).

### 8.1 Statistical Analyses

#### 8.1.1 Primary Effectiveness Endpoint Analyses

The hypotheses for the primary endpoints are that the Informity tool will identify DBS parameters that:

1. Have a larger therapeutic window size compared to programmed parameters at baseline
2. Have a lower TEED compared to programmed parameters at baseline

A comparison of therapeutic window and TEED will be performed for the contact configuration used at baseline, and the contact configuration used after Informity programming with the Informity tool, using a paired t-test. All statistical analyses will be conducted assuming a type-1 error rate of 0.05 unless specifically stated otherwise. The change in TEED from baseline to Informity programming will be used to calculate a corresponding battery longevity projection.

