## 3.0 CLINICAL STUDY DESIGN

This is a prospective, non-randomized, single-arm, multi-center, post-market clinical study designed to evaluate Abbott's Informity tool for Infinity DBS systems.

This clinical study will be conducted at up to 5 centers in the United States.

[figure not shown]
Up to 40 patients will be enrolled in the study. Of these subjects, up to 20 will have PD and up to 20 will have ET. All patients will have received DBS systems prior to enrolling in the study.

The primary and secondary endpoints will be evaluated when all subjects have completed their 6-month follow-up visit.

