### **5.8 Number of Subjects**

Up to 40 subjects will be enrolled in the clinical study in order to analyze the primary endpoints.

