### 8.3 Subgroup Analysis

Subgroup analysis will be performed on the basis of diagnosis (Parkinson's disease or essential tremor). Subgroup analysis will also be performed for those subjects who were programmed with DBS contact 2 or 3 (full ring or individual segments) as a cathode at the Baseline visit.

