## Clinical Investigation Plan

### APPENDIX IX: CIP SUMMARY

Clinical Study Name and Number	ABT-CIP-10245 EVIDENT
Title	Evaluation of the Infinity Deep Brain Stimulation Electrode Screening Mode Tool
Objective(s)	The objective of this clinical study is to characterize the clinical performance of the Informity tool in programming the Infinity DBS system for treatment of Parkinson's disease and essential tremor.
Device Under Investigation	Informity tool on the Clinician Programmer App (Artemis version 3.7 or later)
Number of Subjects Required for Inclusion in Clinical Study	Up to 40 subjects with Parkinson's disease (N=20) or essential tremor (N=20)
Clinical Study Design	Prospective, non-randomized, single-arm, multi-center, post-market clinical study
Primary Endpoints	
 
1) Change in therapeutic window size at the Informity programming visit compared to baseline
 
2) Change in TEED at the Informity programming visit compared to baseline
 

Secondary Endpoints	
 
1) Change in UPDRS III for PD subjects or Fahn-Tolosa-Marin tremor rating scale for ET subjects at, 3 and 6 month follow-up visits compared to baseline
 
2) Change in quality of life measurement as measured by the PDQ-39 for PD subjects or QUEST for ET subjects at the 3- and 6-month follow-up visits compared to baseline
 
3) Duration of programming at the Informity programming visit compared to the most recent programming session prior to enrollment
 
4) Change in TEED at the 3- and 6-month follow-up visits compared to baseline
 

Subject Follow-up	3- and 6-month site visits
Inclusion Criteria	
Parkinson's Disease Patients
 
 
1) Patient must provide written informed consent prior to any clinical study related procedure.
 
2) Patient is 18 to 80 years of age.
 
3) Patient is diagnosed with Parkinson's disease for at least 4 years according to standard practice.
 
4) Patient is willing to maintain a constant dose of anti-Parkinson's disease medication indicated as best medical management for at least 1 month prior to study enrollment.
 
5) Patient is willing and able to comply with the follow-up schedule for the length of the study.
 

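### The primary paired t-tests ignore diagnosis: valid, but conservative if mean change differs between PD and ET, and a diagnosis term recovers that loss for one degree of freedom

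*Combined protocol and SAP*

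**What the plan says.** Section 8.1.1 gives one analysis for each of the two primary endpoints. The baseline configuration is compared with the one chosen by the tool ("and the contact configuration used after Informity programming with the Informity tool, using a paired t-test"). It names no diagnosis term, stratification or weights, so pooling is implied. On the error rate it says "All statistical analyses will be conducted assuming a type-1 error rate of 0.05 unless specifically stated otherwise". Sidedness is not stated, although the hypotheses are directional.

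Section 3.0 sets the enrolment by diagnosis: "up to 20 will have PD and up to 20 will have ET". Section 5.8 adds "Up to 40 subjects will be enrolled in the clinical study in order to analyze the primary endpoints". These are maxima. Appendix IX writes N=20 beside each diagnosis, still under a total of up to 40. Withdrawn subjects are not replaced (Section 5.5) and missing data are not imputed (Section 8.5).

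Diagnosis does appear later in the analysis plan: "Subgroup analysis will be performed on the basis of diagnosis" (Section 8.3). The introduction to Section 8.0 says that poolability and subgroup analyses may be held in a separate SAP. No section says how the overall primary result is to be read if PD and ET differ.

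**The concern.** Diagnosis is built into the design. The two groups have different diseases and brain targets and separate enrolment caps. Given the number enrolled in each group, the gap between the two mean changes is not sampling error. A one-sample SD of change counts it as if it were, so the standard error is too large whenever the gap is not zero.

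There is some reason to expect a gap for TEED. Section 6.2.1 defines it for the whole system, and Section 2.2.2 gives bilateral stimulation for PD but unilateral or bilateral for ET. If TEED is summed over leads, which the documents do not say, lead count alone could make the mean changes differ.

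At stake is some power on both primary tests and the reader's ability to see what the overall mean consists of.

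**Working it through.** **Inputs.** From the documents: a paired t-test, alpha 0.05, and caps of 20 PD and 20 ET. The plan gives no effect size, SD of change, power or sample-size calculation, so it has no figure to reproduce. Assumed: two-sided testing, the same within-diagnosis SD of change in both groups (set to 1), and a difference d between the diagnosis mean changes, in SD units, from 0 to 1.5.

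**Step 1: what pairing removes.** Each subject is differenced before testing, so a PD/ET difference in level cancels. In a check with a 5-unit level shift the paired t statistic was 3.293 with and without it. Only a difference in mean change matters.

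**Step 2: the error term.** With PD share p and n subjects, the expected pooled variance of change, relative to the within-diagnosis variance, is 1 + p(1−p)d²·n/(n−1). At 20/20 this is 1 + (d²/4)(40/39). For d = 1 it is 1 + 0.25 × 1.0256 = 1.256, and the SD ratio is √1.256 = 1.121.

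**Step 3: power at 20/20.** The overall mean change is set at 0.454 SD, which gives 80% power at n = 40 when d = 0. The adjusted test divides the same mean by s_w/√n on n−2 df, where s_w² = [(n₁−1)s₁² + (n₂−1)s₂²]/(n−2). Results are from 100,000 simulated trials per row.

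| d | Variance ratio | SD ratio | Power, pooled | Power, adjusted |
|---|---|---|---|---|
| 0 | 1.000 | 1.000 | 79.9% | 79.9% |
| 0.25 | 1.016 | 1.008 | 79.6% | 80.0% |
| 0.5 | 1.064 | 1.032 | 78.2% | 80.0% |
| 1.0 | 1.256 | 1.121 | 72.6% | 80.0% |
| 1.5 | 1.577 | 1.256 | 63.1% | 80.0% |

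When the overall mean change is zero at 20/20, the pooled test rejects in 4.4% of trials at d = 0.5 and 2.8% at d = 1, so it is conservative. When neither diagnosis changes, it rejects in 5%.

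**Step 4: unequal accrual, observed weights kept.** At d = 0, power is 67.3% pooled and 67.1% adjusted at 20/10, and 58.8% and 58.7% at 20/5. At d = 1 and 20/10 it is 86.5% and 90.7%. The point estimate is the same in both tests.

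**Step 5: the enrolled mix.** The observed-weight mean differs from the equal-weight mean by (p − 0.5)d. At 20/10 this is (0.667 − 0.5)d = 0.167d, or 0.083 SD at d = 0.5 and 0.167 SD at d = 1. At 20/5 it is (0.8 − 0.5)d = 0.30d. At 20/20 it is zero.

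**Step 6: equal weights as an alternative.** The variance is (1/4)(1/n₁ + 1/n₂) instead of 1/n. At 20/10 that is 0.0375 against 0.0333, a ratio of 1.125, and power at d = 0 falls from 67% to 62%. At 20/5 it is 0.0625 against 0.04, a ratio of 1.56, and power falls from 59% to 41%. With a common residual SD, no change in either diagnosis and an ET SD 1.5 times the PD SD, the type I error at 20/10 is about 8.5% to 8.7%. The observed-weight adjusted test stays near 5%; its worst case examined was about 6%, at 20/5 with the ET SD doubled.

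**The case against.** The case for leaving the plan alone is substantial. A one-sample test of mean change in the enrolled population is valid, and the stated objective is only to characterise performance in PD or ET. Pairing already removes level differences. At d = 0.5 the loss is 2 points and on the safe side. The larger values of d need very uneven effects: with an overall change of 0.454 SD, d = 1 means +0.95 and −0.05, and d = 1.5 means +1.20 and −0.30, so one diagnosis would get worse. In such cases the analysis by diagnosis in Section 8.3 is the result to read, and a separate SAP might address poolability. All of this stands, and it limits the point to a modest one. It does not remove it, because a subgroup analysis does not change the SD used in the primary test.

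A reader might go further and infer that the changing PD:ET mix makes the primary result wrong and that the two diagnoses should be weighted equally. If the equal-weight mean is truly zero and d = 1, the pooled test does reject in 10.1% of trials at 20/10 and 25.1% at 20/5. But the documents nowhere ask for an equal-weight mean. These rejections concern a different estimand and are not type I errors of the planned test. As Step 6 shows, equal weighting also has costs of its own.

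**Conclusion.** The point holds as an optional, low-cost improvement. The planned test is valid, and its level is 5% when neither diagnosis changes. It is conservative to the extent that mean change differs by diagnosis. Under the Step 3 assumptions at 20/20, the loss is nil if the diagnoses change alike, about 2 points at d = 0.5 and about 7 at d = 1.0. Nothing in the documents fixes d, so no loss of power can be stated as fact.

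The dependence of the overall mean on the enrolled mix is a matter of interpretation. It is handled by showing the two diagnosis-specific means beside the overall one.

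**What to change.** In Section 8.1.1, replace the paired t-test for each primary endpoint with a linear model of the within-subject change, with diagnosis as a factor centred at the observed PD and ET shares. The intercept is then the overall observed-weight mean change, equal to the paired t-test mean at any split. Test it against zero with the within-diagnosis residual SD on n−2 df. Report the PD and ET mean changes with 95% CIs beside it, without making them further primary tests.

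An equal-weight mean may be given as a sensitivity analysis, but should not be the primary test.

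The cost is a sentence or two in Section 8.1.1 and one degree of freedom. In the simulations the power given up was never more than 0.2 points. No extra data are needed, because diagnosis is known for every subject.
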